5 OBJECTIVES & HYPOTHESES

5.1 *Objective*

The study purpose is to demonstrate safety and effectiveness of the Nerivio Migra electro stimulation device for treatment of migraine attacks with and without aura.

5.2 *Hypothesis*

The hypothesis is that the electro stimulation delivered transcutaneously to the peripheral nervous system at onset of a migraine headache will abort the attack, as indicated by significant difference between proportions of responders to the sham control stimulation and the active treatment without unexpected device related adverse effects.

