7 STATISTICAL CONSIDERATIONS

7.1 *Study Design and Aim*

The study is designed as a prospective, randomized, double-blind, sham controlled multi-center clinical trial. The study aim is to demonstrate safety and effectiveness of Nerivio Migra electro stimulation device for treatment of migraine attacks with and without aura.

7.2 *Study Variables*

7.2.1 *Primary performance variable*

The primary performance endpoint, the proportion (%) of patients reporting freedom from pain (pain grade 0) 2 hours post treatment without rescue medications in at least 50% of treated attacks, will be measured in the form of a binary variable which will be assigned the value of "1" if the subject reports freedom from pain (pain grade 0) 2 hours post treatment without rescue medications in at least 50% of his/her treated attacks, and "0" otherwise.

7.2.2 *Secondary performance variables*

The secondary performance endpoints will all be expressed in the form of binary variables as in the representation of the primary performance variable.

7.2.3 *Exploratory performance variables*

The exploratory performance endpoint, the proportion (%) of patients reporting freedom from pain (pain grade 0) 48 hours post treatment without rescue medications in at least 50% of treated attacks, will be measured in the form of a binary variable which will be assigned the value of "1"

if the subject reports freedom from pain (pain grade 0) 48 hours post treatment without rescue medications in at least 50% of his/her treated attacks, and “0” otherwise.

Patient global impression of change is measured via a questionnaire.

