7.4 Sample Size Estimation

The sample size for this study was calculated to test the above described null hypothesis with a chi-squared test, even though the final analysis may employ a regression model.

In the pilot study, the percentage of responders in the relevant treatment arm was 30%, while the percentage of responders in the sham group was 6%. The latter result is consistent with sham response rates referenced in IHS Guidelines for Migraine Trials. Sample size calculations are based on a more conservative estimate of the sham group response rate of 10%, then a sample size to detect a difference between treated and sham groups (of 20%) with 80% power at a 5% level of significance will result in a total of 124 evaluable subjects, with 62 subjects randomized to the treated arm and 62 to the sham arm. Allowing for a ~10% drop-out rate, a total of 136 (68 treated vs. 68 sham) subjects may be enrolled in the study.

Statistical considerations require availability of 124 evaluable subjects, i.e. with data available for analyses. The study recruitment will be monitored closely via the EDC system and, as soon as the evaluable data target is achieved, the Study Monitor will receive notification. If the number of subjects enrolled in the US is at least 50% of the accumulated population, recruitment will be stopped.

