7.8 Statistical Analyses

Amendments to the statistical analyses section will not require IRB approval, unless driven by protocol or study design change. In that case a standalone SAP will be prepared prior to data lock for each analysis milestone.

7.8.1 *General Considerations*

Statistical analyses will be performed using SAS® v9.4 (SAS Institute, Cary NC, USA).

All statistical tests will be two-sided. The required significance level of findings will be equal to or lower than 5%, nominal p-values will be presented. Where confidence limits are appropriate, the confidence level will be 95%.

Continuous variables will be summarized by a mean, standard deviation, minimum, median and maximum, and categorical variables by a count and percentage. For comparison of means (continuous variables), the two-sample t-test or the Wilcoxon rank sum test will be used as appropriate. For comparison of proportions (categorical variables), the Chi-squared test or Fisher's exact test will be used as appropriate.

If multiple measurements are taken in a single patient, statistics described below will be appropriately modified to accommodate the within patient correlation.

7.8.2 *Significance levels and handling of type I error*

7.8.2.1 *Type I Error*

The overall significance level for this study is 5% using two-tailed tests, except for treatment by site interaction that will be tested at a significance level of 10%.

7.8.2.2 *Hierarchy Approach for Secondary Endpoints Analysis*

The hierarchy approach will be adopted for the primary and secondary endpoints to control type I error due to multiple endpoint testing. Thus, the primary endpoint will first be analyzed and only if $p < 0.05$, will the secondary endpoints be analyzed.

7.8.3 *Demographic and Other Baseline Characteristics*

Demographic and baseline condition related characteristics will be tabulated and compared between the study groups by data type. Continuous variables will be summarized by a mean, standard deviation, minimum, median and maximum, and categorical variables by a count and percentage.

This data will include:

- Demographic data
- Medical history
- Migraine preventive medication
- Other concomitant medication
- Migraine attacks characteristics per ICHD-3 diagnostic criteria for migraine with and without aura
- Physical examination
- Laboratory (pregnancy) tests for women of childbearing potential

7.8.4 *Disposition of Patients*

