Patient global impression of change will be summarized by descriptive statistics per treatment group and compared between the groups with a t-test.

Ease of use will be summarized by descriptive statistics.

7.8.6 *Safety Analysis:*

The primary safety variable, the cumulative incidence (and 95% CI) of device related adverse events (AEs) throughout the study, will be presented in tabular format and will include incidence tables by severity.

Adverse event rates will be compared between the study groups with a chi-squared test.

Serious adverse events will be listed and discussed individually.

Treatment tolerability will be compared between the study groups, the number and percent of subjects who fail to complete the study and the number and percent of subjects who fail to complete the study because of Adverse Events will be presented as well.

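### Section 7.8.6 compares adverse event rates between arms by a chi-squared test alone, with no interval for the active-minus-sham difference, in a trial sized only for pain freedom

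*Combined protocol and SAP*

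**What the plan says.** Section 7.1 states: "The study aim is to demonstrate safety and effectiveness of Nerivio Migra electro stimulation device". Section 5.1 has the same purpose, and the hypothesis in 5.2 adds the condition "without unexpected device related adverse effects". The synopsis names device-related adverse effects as the primary safety endpoint.

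Section 7.8.6 carries this out as follows:

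- The primary safety variable is the cumulative incidence of device-related AEs over the study, with a 95% CI and tables by severity. The text does not say whether the CI is for each arm or for both together.
- Between arms: "Adverse event rates will be compared between the study groups with a chi-squared test".
- Serious events are listed and discussed one by one.
- Tolerability is compared between groups (no method named), and discontinuations, overall and due to AEs, are counted.

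No between-arm risk difference, interval for it, acceptable rate or safety decision rule appears. Section 7.7.4 makes ITT the main safety set. Section 7.4 sets the size from the performance endpoint alone, and the success rule in 7.8.5 uses performance alone.

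**The concern.** A chi-squared p-value does not say how large an excess of AEs the data leave open. When a trial is sized for a 20-point difference in pain freedom, a smaller but still relevant excess of device effects can easily give p > 0.05. If the report then has only that p-value for the between-arm comparison, a reader cannot tell evidence of a small difference from an absence of evidence.

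The per-arm incidence matters as well. Sham devices look identical and deliver perceivable pulses (6.1), and 14.7 rates minor skin irritation from wearing the device as likely. Such effects can occur in both arms, so a comparison with sham says little about how often active users have them. A CI that pooled the arms would not describe active users either. Section 7.8.5 does specify an exact 95% CI for each group for pain freedom; the safety text does not.

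**Working it through.** **Inputs from the documents.** Two-sided 5% level (7.8.2.1: "The overall significance level for this study is 5% using two-tailed tests"); 10% vs 30% pain freedom, 80% power, 62 per arm evaluable, 136 enrolled as 68 + 68 (7.4); maximum 248, so 124 per arm (7.5); 1:1 allocation (7.6); ITT for safety (7.7.4).

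**Assumed inputs.** AE rates. The documents give no planning rate and no tolerable excess; the only observed figure is that the pilot reported no device-related events (4.2). A range is therefore shown.

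**Step 1: reproduce the plan's sample size.** With the pooled-variance formula and no continuity correction,

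n per arm = [1.960·√(2·0.20·0.80) + 0.842·√(0.30·0.70 + 0.10·0.90)]² / 0.20² = 1.5697² / 0.04 = 61.6, rounded up to 62.

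This gives 124 in total, matching 7.4: "with 80% power at a 5% level of significance will result in a total of 124 evaluable subjects". Power at 62 per arm is 80.3%. The size is right for its purpose, but that purpose is performance only.

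**Step 2: power of the planned AE test.** For n per arm, sum the product of the two binomial probabilities over all pairs of counts for which the uncorrected chi-squared test has p < 0.05 with active above sham.

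| Sham vs active (assumed) | Excess | 68 per arm | 124 per arm |
|---|---|---|---|
| 2% vs 8% | 6 points | 36% | 60% |
| 5% vs 15% | 10 points | 51% | 77% |
| 10% vs 20% | 10 points | 37% | 61% |
| 5% vs 20% | 15 points | 79% | 96% |

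Section 7.8.1 also allows Fisher's exact test. At 68 per arm its power for the same four rows is lower: 19%, 39%, 29% and 71%.

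**Step 3: what a non-significant result can look like.** Take 5/68 active and 1/68 sham.

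- Difference: 7.35% − 1.47% = 5.88 points.
- Pooled rate 6/136 = 4.41%; z = 0.0588 / √(0.0441·0.9559·2/68) = 1.67; p = 0.095.
- Wilson limits: active 3.18% to 16.09%, sham 0.26% to 7.87%.
- Newcombe lower limit: 5.88 − √[(7.35 − 3.18)² + (7.87 − 1.47)²] = −1.8 points.
- Newcombe upper limit: 5.88 + √[(16.09 − 7.35)² + (1.47 − 0.26)²] = +14.7 points.

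The test reports no significant difference, while the interval still allows an excess of nearly 15 points.

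**Step 4: what zero events would show.** The two-sided exact 95% upper limit for 0/n is 1 − 0.025^(1/n): 5.3% at n = 68 and 2.9% at n = 124.

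**The case against.** The strongest reply is that the safety assessment does not rest on this p-value. The plan leads with an incidence and its 95% CI, tabulates by severity, discusses serious events individually, counts discontinuations, compares tolerability, and adds data monitoring committee review (6.4.6) and adjudication of serious and device-related events (14.8). The protocol describes a non-significant-risk device study (4.3.2), and the effects foreseen in 14.7 are minor and transient. All of this stands. It means that the chi-squared test is neither the only between-arm safety comparison nor the only safety output, and that an upper bound on an incidence is already planned. It does not supply an interval for the between-arm difference, nor say that the planned CI is per arm.

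A reader might infer that the sponsor will treat p > 0.05 as proof of safety. The documents do not say so: no passage gives that meaning to the AE test, and the success rule uses performance alone. The point is a gap that leaves room for misreading, not a stated rule.

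A reader might also infer that the test would miss any relevant excess at least half the time. That depends on assumed rates. At 68 per arm, 5% vs 15% is missed 49% of the time and 5% vs 20% 21%; at 124 per arm, all four scenarios are missed less than half the time.

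Finally, quoting upper limits without a stated acceptable excess does not by itself demonstrate safety. That is fair. The limits show what the trial has excluded, and readers can then judge whether it is enough.

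**Conclusion.** The point holds in this form: the between-arm comparison of AE rates is a test with no estimate or interval, the planned incidence CI is not tied to an arm, and the trial was not sized for safety. Under the assumed rates, power at 68 per arm is 36% to 51% for excesses of 6 to 10 points and reaches 79% only for 5% vs 20%. A non-significant result at the planned size would therefore not exclude an excess of 5 to 10 points.

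These powers rest on assumed AE rates, independent subjects, one yes/no outcome per subject and the uncorrected chi-squared test. The case for an interval does not depend on which of those rates is true. The change should be made, since the stated aim is to demonstrate safety and the data needed are already collected. A reader might go further and ask for the hypothesis in 5.2 to be rewritten; that is not needed, because better reporting in 7.8.6 answers the point.

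**What to change.** In 7.8.6, replace the chi-squared sentence with wording such as:

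*For device-related AEs and for all AEs, in the ITT set, the number of subjects with at least one event will be given by arm with exact (Clopper-Pearson) 95% CIs. The active-minus-sham risk difference will be given with a 95% Newcombe or Miettinen-Nurminen CI. The safety statement will be based on the upper limits of the active-arm incidence and of the risk difference. A non-significant p-value will not be read as evidence of no excess.*

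Zero events among 68 active subjects would then be reported as an incidence of at most 5.3%.

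The cost is a few lines of text and table code, with no new data or patients. The opening of 7.8 allows the statistical section to be amended without IRB approval unless a protocol or design change drives it, and this change alters neither objectives nor endpoints. The one downside is a slightly less favourable safety statement, because an upper limit is quoted where a lack of significance might otherwise have been.

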7.8.7 Handling of Missing Data

A sensitivity analysis of the primary end-point will be performed to assess the impact of missing data on the study outcome using possible imputation methods for binary data. A “worse case” scenario analysis will be performed as well where subjects with missing data for the binary response assessment will be considered as a non-responder/ non-success.

Imputation of missing data may be performed on secondary and exploratory endpoints as well.

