Study Procedures

Potential patients signed informed consent prior to any study procedure. The patient medical history, migraine history, use of concomitant medications and diagnosis were recorded. Patients found eligible by meeting all of the inclusion criteria and none of the exclusion criteria received documented training whereupon its successful completion the investigational device was provided to study participants for home use.

As per the instructions for use, participants were instructed to activate the device at the onset of a migraine attack and manually adjust stimulation intensity to a level where it is perceivable but not painful. Patients were requested to refrain from use of rescue medications prior to and during the first two hours following treatment by the device, and if they could not comply with this, record medications usage in the smartphone application.

Five 20-minute long stimulation protocols were programmed into each unit; four active programs at 100-120 Hz, with primary phase widths of 200 (P200), 150 (P150), 100 (P100) and 50 (P50) microseconds, and one placebo stimulation protocol (P0) at 0.1 Hz frequency with 45 microseconds long pulses. Stimuli were given at random sequences with the following distribution: P0 and P200: probability of 1/3 each, P50, P100, P150: probability of 1/9 each. Randomized sequences of programs were generated independently for each participant.

Both patients and study personnel were blinded to the order of individual treatments.

Via the smartphone application, each participant was asked to rate his/her migraine pain level four times using a Numeric Pain Rating Scale (NPS, values 0-10): (1) upon starting the treatment, (2) during (halfway through treatment program), (3) at the end of treatment, as well as (4) two hours after treatment.

At the beginning of each treatment, participants were asked to provide feedback using the application regarding the time elapsed from start of migraine attack to start of the treatment. In case of failure to provide feedback regarding pain level post-treatment, telephone follow-up was performed by study investigator staff to solicit such feedback. Follow up phone calls were

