performed to record changes in medical condition, concomitant medication, migraine therapy and adverse effects. Unscheduled visits were recorded and termination visit were scheduled upon the completion of the study as defined by a maximal number of 20 complete treatment cycles but no longer than 6 months from enrollment. (whichever is fulfilled first). In the event of premature discontinuation an early discontinuation visit was scheduled. End of study interview was performed soliciting feedback regarding device usability, burden of treatment, use of migraine medications during the study period, as well as free comments.

Study Endpoints

- The primary efficacy endpoint of the study was the proportion of responders, where a responder is defined as subject with clinically significant decrease in pain score measured by Numeric Pain Rating Scale (NPS) of at least 50% 2 hours post treatment as compared to baseline in at least 50% of treatments.
- The second primary performance endpoint was relative pain reduction at 2 hours post treatment as compared to baseline.
- The primary safety endpoint was evidence of device related adverse effects.

Burden of treatment was assessed by mean scores of post-study questionnaire. Success was defined as superior performance of active treatments as compared to sham treatment. The protocol provided for enrollment of up to 100 patients.

Summary of Results

The pilot study was performed between June 2015 and March 2016. A total of 86 participants were provided with the Nervio Migra devices for use as part of this clinical study.

A summary of participants' demographic characteristics is presented in Table 2 below.

	Female	Male
N (%)	69 (80%)	17 (20%)
Age mean (min-max, STD)	45.2 (22-72, 11.7)	48.8 (26- 67, 11.7)
Migraine attacks per month, mean (STD)	5.1 (2.7)	5.34 (2.3)
Mean pain intensity during attack	8.9	8.6
Occurrence of aura	40 (58%)	11 (65%)

Table 2 – Pilot Study Population

Seventy-two participants successfully treated at least one migraine attack. The remainder of participants either did not treat their attacks per protocol, or failed to provide complete feedback. One participant was excluded from statistical analysis due to repeated use of rescue medications concurrently with the electro stimulation treatments. Complete reporting was obtained for 70% of activations for P200, P150, P100 programs, 58% of activations of P50 and 28% of placebo activations.

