7.7 Analysis sets

7.7.1 *Intent to treat analysis set (ITT)*

The ITT analysis set will consist of all subjects randomized. In accordance with the ITT principle, all subjects randomized will be kept in their originally assigned treatment group.

7.7.2 *Modified intent to treat analysis set (mITT)*

The mITT set will consist of all subjects in the ITT set who completed at least one study treatment, assigned a treatment group as treated.

7.7.3 *Per protocol analysis set (PP)*

The Per-Protocol (PP) analysis set includes all patients from the mITT analysis set without any major protocol deviation who have evaluable data on at least one qualifying migraine attack.

7.7.4 *Statistical analysis of analysis sets*

The ITT analysis set will serve as the main set for safety assessments and the mITT set for all performance assessments.

The primary performance assessment will also be performed on the PP analysis set as a sensitivity analysis.

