The numbers of patients who entered the study and completed each stage of the study will be provided per month, as well as the reasons for all post randomization discontinuations, grouped by major reason, e.g., lost to follow-up, adverse event, poor compliance, did not administer any treatment (with reasons). A list of discontinued patients, protocol deviations, and patients excluded from the performance analysis will be provided as well.

7.8.5 *Performance Analyses*

Primary Performance Analyses:

The primary endpoint is freedom from pain at 2 hours post treatment without rescue medications in at least 50% of treated attacks, a count and percentage of subjects free from pain will be calculated and presented for both study groups each with a two-sided 95% exact confidence interval. The groups will be compared with a chi-squared test.

If the null hypothesis is rejected in favor of the alternative hypothesis and the proportion (%) of subjects reporting freedom from pain at 2 hours post treatment without rescue medications in the treated group is greater than that of the sham group, the study will be deemed successful.

The primary endpoint will also be evaluated stratified by center using a Mantel-Haenszel test to assess the center by group interaction.

A sensitivity analysis of the primary end-point will be performed to assess the impact of missing data on the study outcome. This will be performed using several possible imputation methods.

Subset analysis:

Adjustment for other covariates such as demographics or other baseline patient characteristics may be performed by adding these variables into a logistic regression model.

Subgroup analysis according to use of preventive medications will be performed and reported by adding these variables to a logistic regression model.

Secondary performance analyses:

The secondary performance variables will be summarized by a count and percentage and compared with a chi-squared test.

Exploratory performance analyses:

A count and percentage of patients reporting freedom from pain (pain grade 0) 48 hours post treatment without rescue medications in at least 50% of treated attacks will be presented, the groups will be compared with a chi-squared test.

Use of rescue medications will be summarized by descriptive statistics per treatment group and compared between the groups with a t-test.

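### The planned 'worse case' analysis fails missing subjects in both arms, so it is not a worst case for superiority and favours the device if sham subjects report less

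*Combined protocol and SAP*

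**What the plan says.** Section 7.8.7 promises a sensitivity analysis of the primary endpoint and labels one version a worse case: "subjects with missing data for the binary response assessment will be considered as a non-responder/ non-success". The rule is the same in both arms. The other methods are left open in Section 7.8.5: "This will be performed using several possible imputation methods".

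The primary variable (Section 7.2.1) scores 1 if the subject reports pain freedom "2 hours post treatment without rescue medications in at least 50% of his/her treated attacks", and 0 otherwise. The plan does not say whether a treated attack with no 2-hour report stays in that denominator.

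Two other sections bear on who counts. Section 7.4: "Statistical considerations require availability of 124 evaluable subjects, i.e. with data available for analyses". Section 7.7.2, defining the set used for performance: "The mITT set will consist of all subjects in the ITT set who completed at least one study treatment". The second has no reporting requirement.

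The pilot summary in Section 4.2 gives the only reporting rates in the document: "Complete reporting was obtained for 70% of activations for P200, P150, P100 programs, 58% of activations of P50 and 28% of placebo activations".

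**The concern.** A worst-case analysis should ask whether a positive result survives the assumptions least favourable to the claim. For superiority over sham, these are that missing active subjects failed and missing sham subjects succeeded. Failing everyone does the first and reverses the second. The result is roughly neutral when missingness is equal. When sham subjects report less, the analysis takes more potential responders from sham than from active and so moves towards the device.

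The pilot makes that direction plausible. Programs were given in random sequence within participants, and telephone follow-up was already used, yet placebo activations were fully reported far less often than active ones.

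The stake is the reading of a positive primary result: an analysis meant to challenge it could strengthen it. The attack-level gap reaches further. If unreported attacks count as failures in the primary variable, the primary test itself is affected.

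**Working it through.** **Inputs.** From the plan: 62 per arm, 30% against 10% responders, two-sided 5% and 80% power (Section 7.4; two-sided tests, Section 7.8.1); chi-squared test (Section 7.8.5); up to four treated attacks per subject (Synopsis); pilot reporting of 70% and 28% (Section 4.2). Assumed: the missingness rates below, and true responder rates of 10%, 20% and 30% in both arms under no effect. Only 10% is the plan's sham figure.

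**The plan's own figure.** n = [1.96·√(2·0.20·0.80) + 0.8416·√(0.10·0.90 + 0.30·0.70)]² / 0.20² = 61.6, so 62 per arm, as stated. The uncorrected chi-squared test is therefore used below, by exact enumeration of two binomials with 62 per arm.

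**1. The Section 7.8.7 rule at subject level.** Observed rate = true rate × (1 − missing). For example, at a true 20% with 10% and 30% missing: 0.20 × 0.90 = 18% active, 0.20 × 0.70 = 14% sham. Chance of significance in favour of the device (nominal 2.5%):

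| Missing, active / sham | True 10% | True 20% | True 30% |
|---|---|---|---|
| 10% / 10% | 2.5% | 2.3% | 2.5% |
| 5% / 15% | 3.9% | 4.5% | 5.6% |
| 10% / 30% | 6.0% | 8.3% | 11.7% |

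**2. The attack-level rule.** Assume four independent attacks, per-attack success p with P(Bin(4, p) ≥ 2) equal to 10%, 20% or 30% (p = 0.143, 0.212, 0.272), and per-attack reporting rate r. At the pilot rates, the share of subjects with no report is 0.30⁴ = 0.8% on active and 0.72⁴ = 26.9% on sham. Three readings:

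- A: fail only subjects with no report and leave other subjects' status unchanged: true rate × (1 − (1 − r)⁴).
- B: score on reported attacks only, and fail subjects with none: Σₖ P(Bin(4, r) = k) · P(Bin(k, p) ≥ k/2), k = 1 to 4.
- C: count every unreported treated attack as a failure: P(Bin(4, p·r) ≥ 2).

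At a true 20% and 70% against 28% reporting, the resulting rates are A 19.8% against 14.6%, B 21.2% against 19.0%, C 10.8% against 2.0%. Chance of falsely favouring the device at true 10/20/30%:

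| Reporting, active / sham | A | B | C |
|---|---|---|---|
| 70% / 28% (pilot) | 7/11/17% | 2/5/9% | 25/54/76% |
| 85% / 65% (assumed) | 2.7/2.6/2.8% | 0.5/0.7/1.1% | 9/16/22% |

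C is one reading of Section 7.2.1, not the Section 7.8.7 rule. Under B at 85% against 65% the direction reverses, towards sham.

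**3. A worked example (assumed counts).** Active 17 of 61 responders with 1 missing; sham 5 of 45 with 17 missing.

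- Complete cases, 17/61 against 5/45: χ² = 4.42, p = 0.035.
- Section 7.8.7 rule, 17/62 against 5/62: χ² = 7.96, p = 0.005.
- If 4 of the 17 missing sham subjects responded (24%, against 28% observed on active), 17/62 against 9/62: χ² = 3.12, p = 0.078.

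The analysis labelled as the harshest gives a stronger result than the complete cases.

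**The case against.** **Pilot rates.** They come from a cross-over and are per activation. They describe complete feedback when "each participant was asked to rate his/her migraine pain level four times", not the single 2-hour rating that matters here. This trial also adds automated detection of missing reports and queries to participants (Sections 6.4.4 and 6.4.5). All of this stands: the pilot supports a direction, not a size, and the gap may shrink. It does not turn the rule into a worst case.

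**Base rates.** The plan's sham rates are 6% (pilot) and 10% (planning). At 10%, reading B gives 2% even at the pilot rates and 0.5% at 85% against 65%, so there is no inflation. Reading A could not be computed from real data, because partial reporters keep a status nobody observed. These points limit the attack-level figures. They leave the first table's 10% column, where the inflation is modest: 3.9% and 6.0%.

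**The example.** It is chosen to illustrate. With 2 of 17 missing sham responders, close to the observed sham rate of 11%, p = 0.023; with 3 of 17, p = 0.044. Significance is lost only at a rate about double the observed one. A tipping-point display would show exactly this, and the planned analysis cannot.

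**Role and location.** This is one supportive analysis, its rule is stated openly, and success rests on the primary test. Section 6.2 foresees a detailed analysis plan, which Section 9 lists as a separate document and which could hold the missing rules. That is possible, but the visible text names no other method. The per-protocol set requires evaluable data on at least one attack (Section 7.7.3), so it cannot address subjects without reports.

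**Conclusion.** The concern holds. Coding missing as non-response in both arms is not a worst case for superiority if any sham subject is missing, and it favours the device when sham reporting is poorer and some missing sham subjects would have responded. For assumed gaps of 5% against 15% and 10% against 30%, the chance of falsely favouring the device rises from 2.5% to 3.9–5.6% and 6.0–11.7%. There is no inflation if missingness is equal or if the missing subjects were true failures.

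The effect on trial success is indirect unless unreported attacks are also failed in the primary variable. On that reading the primary test could be materially biased, but the plan does not say whether it applies. Read literally, Section 7.2.1 would make an unreported attack a failure, and then the binary response of a treated subject could never be missing, which does not fit Section 7.8.7. This should be fixed before any unblinded look. Confidence in the size is moderate, because this trial's reporting rates by arm are unknown.

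**What to change.** 1. In Section 7.2.1, state how a treated attack without a 2-hour report counts, and how an mITT subject with no report is handled in the main analysis.
2. Tabulate 2-hour reporting by arm.
3. In Section 7.8.7, pre-specify a tipping-point grid over arm-specific success rates among missing data, at attack and subject level. Its extreme corner is active failure with sham success.
4. Keep missing as non-responder as an ordinary sensitivity analysis, without the worse-case label.

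The cost is one paragraph in the analysis plan, one sentence in the primary variable definition and a little programming. Design and sample size do not change.

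The drawback is that the extreme corner will look unfavourable. At the design effect with 10% missing per arm it compares 0.30 × 0.90 = 27% with 0.10 × 0.90 + 0.10 = 19%, for a power of 18%. With 5% missing the power is 47%, against 81% by exact enumeration with complete data. It should therefore be read as the edge of the grid and not as a test the trial must pass.
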